Cerebrovascular disease	Lee 1999, Kheterpal 2009, Botto 2014

Peripheral vascular disease	Botto 2014
Diabetes	Lee 1999 (Insulin-dependent), Botto 2014 (though not found to be predictive in Kheterpal 2009)
RCRI	Lee 1999
Hypertension	Kheterpal 2009 (hypertension requiring medication), Botto 2014, Ruetzler 2020 (4)
Kidney function (laboratory)	Lee 1999, Botto 2014 (though not found to be predictive in Kheterpal 2009)
BNP / NT-proBNP	Choi 2010 (13), Rodseth 2013 (14) and 2014 (15) metanalyses, Malhotra 2016 (16), Duceppe 2020 (17)
Anemia	Feng 2017 (18)
Heart rate	Abbott 2016 (>96) (19), Laitio 2004 (increased variability) (20), Devereaux 2011 (every increase by 10 from baseline) (21)
American Society of Anesthesiologist physical status	House 2016

Table 2. Intraoperative factors studied in literature associated with MINS and/or major myocardial complication and mortality

Variable	References
Type and risk of surgery (various definitions)	Lee 1999, Boersma 2005 (22), Davenport 2007 (23) Not found to be predictive in Kheterpal 2009 likely due to different definitions and study populations.
Emergency surgery	Detsky 1986 (24), Boersma 2005, Kheterpal 2009, Botto 2014, House 2016, Zhao 2017 (25), House 2016 Emergency surgery patients excluded in RCRI (Lee 1999)
Red blood cell (RBC) transfusion	Kheterpal 2009, Whitlock 2015 (26), Wu 2010 (27), Glance 2011 (28), Devereaux 2011

Hypotension (mmHg)	Wesselink 2018 (29), Sessler 2018 (30)
Tachycardia (beats)	House 2016 (>100 beats for >59 minutes), Abbott 2018 (>100)

Table 3. Postoperative factors studied in literature associated with MINS and/or major myocardial complication and mortality

Variable	References
Postoperative hypotension	van Lier 2018 (quartiles, 3 days postoperatively) (31), Sessler 2018 (<90mmHg, 4 days postoperatively) Liem 2020 (duration MAP <75, 24 hours postoperatively) (32)
Acute kidney injury	Zhao 2017
Vasopressor use 24 hours after surgery	Zhao 2017

Objectives

1. To develop and internally validate a model that uses the duration and degree of intraoperative and postoperative hypotension to predict the daily maximum troponin level from postoperative days zero to two, in a high risk population where troponin monitoring was ordered.

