***A priori* features in the primary model**

This *a priori* list of predictors will be used for the primary modeling in Objective 1: duration hypotension (summarized as a percentage of duration of MAP<75 mmHg in the duration of time modeled, e.g. postoperative day 0, 1, and 2), age, sex, emergency surgery, RCRI, and postoperative GFR, as well as the postoperative day and the interaction between postoperative day and % duration MAP<75mmHg as detailed below.

Statistical analysis

Missing data

We will exclude patients with no intraoperative or postoperative vital signs and no troponin measurements from the cohort. Complete case analysis will be performed for vital sign features, with each complete case defined as a patient with ≥ 1 vital sign measurement(s) and ≥ 1 troponin measurement(s). Since the frequencies of measurements are different, missing vital signs are not considered missing values for inclusion/exclusion purposes as long as patients meet the complete case criteria. No imputation will be performed for vital sign data.

For features that are not vital signs (e.g. age, sex), we anticipate minimal missing data (as these variables are routinely collected), and assume missing at random. Due to the longitudinal data structure with correlated observations, we opted for a simpler method of imputation for the primary analysis. For features missing $< 1\%$, complete case analysis will be

performed; between 1-<10%, multiple imputation; above 10%, the feature would be excluded from the model and the reason for missing data will be investigated.

Data quality

The data quality of the CIHI vs. chart review results of the comorbidity information will be assessed by Pearson correlation, with chart review as the gold standard.

Cohort characteristics

Continuous data will be presented in mean (SD) if normal, and median (IQR) if non-normally distributed. Categorical data will be presented as frequency (%). The following characteristics will be presented as overall group, and stratified by MINS vs. no MINS:

- Age
- Gender
- American Society of Anesthesiologists' physical status classification (ASA)
- Type of anesthesia (general, neuraxial, peripheral, and/or sedation)
- RCRI score and categories: pre-existing TIA/CVA, insulin dependent diabetes, serum creatinine >177 mmol/L, coronary artery disease, congestive heart failure, and high risk surgery including intrathoracic, intraabdominal or suprainguinal vascular surgery

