- Charlson Comorbidity Index (CCI) score and categories: history of MI, CHF, PVD, CVA/TIA, dementia, chronic pulmonary disease, connective tissue/rheumatic disease, peptic ulcer disease, liver disease, diabetes mellitus, hemiplegia/paraplegia, moderate to severe CKD, local/metastatic malignancy, AIDS/HIV
- Surgical service
- Duration of surgery
- Surgical priority: emergent/urgent vs. elective
- ICU admission preoperatively
- Cardiovascular medications preoperatively: Angiotensin II receptor blockers (ARBs), angiotensin-converting enzyme (ACE) inhibitor, and beta blockers (based on available names extracted from Cerner; may be missing medications that have been held and not restarted in hospital).
- Estimated blood loss
- Use of intraoperative/postoperative vasopressors/inotropes
Yes/no (received anything at all)
Small amount of intraoperative use (phenylephrine (<200 mcg) or ephedrine (<10 mg))
Significant only (i.e. exclude if small doses of phenylephrine (<200 mcg) or ephedrine (<10 mg))
- Laboratory preoperatively (30 days before surgery): NT-proBNP, hemoglobin, creatinine/GFR, troponin
- Respiratory rate
- Postoperative disposition (ward vs. HAU vs. ICU) - multiple entries possible; time of moving in/out of each unit
- Descriptive statistics of troponin as a continuous variable by postoperative days

- Diagnosis of myocardial infarction, MINS, and postoperative myocardial injury
- MINS troponin monitoring
 - o Duration (operative day to the last day of troponin measurement)
 - o Numbers of troponin testing done and frequency
 - o Time of MINS diagnosis (rule in vs. rule out), hours after end of operation as defined by the event of patient leaves the operating room
- Non-MINS causes of troponin elevation
 - o PE/DVT
 - o Sepsis
 - o Rapid atrial fibrillation
 - o Cardioversion < 24 hours
 - o Chronic elevation (excluded)
- Vitals monitoring
 - o Frequency (plot frequency vs. POD)
 - o Duration within POD3
- 30 Day in-hospital mortality

Also, descriptive summaries of the vital statistics as listed in Table 4 will be presented.

Data processing

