The Cerner, Surginet, and chart review data will then be linked by de-identified Cerner study ID. The time series time stamps will be shifted to have the start of surgery as 00:00, Jan 1, 2020, in order to standardize the times for longitudinal modeling. Data will then be processed for removal of vital sign artefacts per the Multicentre Perioperative Outcomes Group protocol (35). To generate a final blood pressure dataset, if noninvasive blood pressure and invasive blood pressure are available during the same minute, then the measurement that is 1) not marked as artefact and 2) has a higher systolic blood pressure will be taken. Data will also be processed for calculation of RCRI, determination of the timing of MINS diagnosis, truncation of vital sign time series to the appropriate time stamp (see below), and calculation of duration under threshold of the time series to create vital sign summary variables as described in Table 4 for each postoperative day (0-<24h, 24-<48, 48-<72, and <72-96h after surgery end time). A formal chart review will also be performed to extract data not automatically retrieved from Cerner and Surginet, and verify data quality of automatically extracted comorbidities.

For modeling troponin as a continuous outcome, the vital sign time series will be truncated at the last troponin measurement within 3 days of surgery. For modeling the binary MINS outcome definitions the data will be truncated at the time of troponin laboratory diagnosis of the outcome event, postoperative day 3 (since the MINS protocol monitors for 3 days) or hospital discharge or death, whichever occurs first. All time measurements will be standardized as above in relation to the surgery start time.

Predictive Modeling Approaches

Approach I. Analysis using conventional longitudinal modeling (primary objective)

Data visualization

The initial exploratory analysis of the vital signs and troponin data involves time series visualizations and summaries to explore any potential patterns present in the data that may be associated with troponin quantiles or MINS or myocardial injury diagnosis. Spaghetti plots of the longitudinal data will be created for the outcome and vital signs variables, with lines colour-coded by troponin quantiles or MINS or myocardial injury diagnosis. Other relevant visualizations (scatterplots, boxplots, etc.) examining the associations between the troponin outcome and the vital signs variables will also be created.

Primary Modeling

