The primary analysis will involve building a linear mixed effects model (with random intercepts) to predict the maximum daily troponin level between postoperative days 0 to 2 as the continuous outcome. The postoperative days 0, 1, and 2 accounts for approximately 40%, 40%, and 10% of MINS, respectively (4). Due to the limitations in retrospective data and the daily troponin monitoring, we will use day as a unit for time rather than hour to avoid overestimation of precision by readers.

For the primary and secondary models described in Objectives 1 and 2, an *a priori* list of predictors will be used: duration hypotension (summarized as a percentage of duration of MAP<75 mmHg in the duration of time modeled, e.g. postoperative day 1) age, sex, emergency surgery, RCRI, and postoperative GFR, as well as the postoperative day and the interaction between postoperative day and % duration MAP<75 mmHg as detailed below.

For longitudinal modeling, the vital signs data and troponin data will be aggregated to the day level, so that the model can predict at the daily temporal level. If there are multiple troponin measurements on the same day, the maximum will be taken. This aggregation of the data is necessary to account for the fact that the vital signs and troponin measurements are measured at irregular intervals (both across patients and data types), often due to the acting physician's response to the patient's condition. Additionally, due to this characteristic of the raw data, the vital signs predictors will be created such that they are standardized to be robust to the number of daily measurements performed (for example, by taking the percentage of day duration, NOT the total duration, of blood pressure below a specific threshold across all measurements during that day). A categorical time variable (representing the day of the measurement) will be included as a predictor within the model.

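### Daily windows counted from surgery end leave intraoperative hypotension out of the only hypotension predictor in the primary model, contrary to Objective 1

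*Combined protocol and SAP*

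**What the plan says.** - **Objective 1** sets the task for the primary model: it "uses the duration and degree of intraoperative and postoperative hypotension to predict the daily maximum troponin level from postoperative days zero to two".
- **A priori features in the primary model** lists one hypotension variable, "summarized as a percentage of duration of MAP<75 mmHg in the duration of time modeled, e.g. postoperative day 0, 1, and 2", plus its interaction with day. Primary Modeling repeats this list, and the example equation there has blood-pressure terms for Days 0, 1 and 2 only.
- **Data processing** computes time under threshold "for each postoperative day (0-<24h, 24-<48, 48-<72, and <72-96h after surgery end time". The same section says "The time series time stamps will be shifted to have the start of surgery as 00:00, Jan 1, 2020", and its next paragraph, on truncation, closes with "All time measurements will be standardized as above in relation to the surgery start time".
- **Primary Modeling** says "the vital signs data and troponin data will be aggregated to the day level". It gives no hour limits for the troponin day.
- **Vital sign candidate features** and **Table 4** provide for intraoperative, postoperative and combined versions of the summaries. **Secondary, Sensitivity, and Exploratory Analyses** lists the two single-period versions as changes to the primary analysis.
- **Outcome** times MINS diagnosis from surgery start. **Cohort characteristics** reports it in "hours after end of operation as defined by the event of patient leaves the operating room".
- **Data Dictionary** extracts both times. Entering the operating room starts the time series, and leaving it starts the postoperative series.

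**The concern.** The daily percentage is the only route by which hypotension reaches the primary model. If its windows open when the patient leaves the operating room, what happened during surgery has no route in. The primary model would then answer a narrower question than Objective 1 asks. It would coincide with the planned postoperative-only variant, and Objective 3 could not judge whether one period alone suffices, because no combined-period model would exist to compare with. The intraoperative-only variant would have no day window at all.

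The second issue concerns the outcome. Predictor and troponin are paired by day, but only the vital-sign day has stated hours. Two analysts following the text could label the same troponin differently.

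**Working it through.** The plan gives no figure to reproduce here. The check is where each minute falls under each origin.

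**Inputs.** The windows and both origins come from Data processing, and the operating-room times from the Data Dictionary. The documents give no length of surgery, so L (hours) is assumed to lie between 1 and 8.

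**Step 1: intraoperative minutes.** Let t be hours since surgery start, with 0 ≤ t < L during surgery. Measured from surgery end, the time is t − L, which is below 0 for every such t. The first window opens at 0, so no intraoperative minute falls in any window, for any L. With windows counted from surgery start, all of them fall in Day 0 whenever L is under 24 h.

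**Step 2: effect on the predictor.** As an illustration, assume that MAP is below 75 mmHg for one third of surgery and never afterwards, with fully observed windows. The Day 0 percentage is then:

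| L | Windows from surgery end, as written | Windows from surgery start: (L/3)/24 | Day 0 from surgery start to 24 h after end: (L/3)/(24 + L) |
|---|---|---|---|
| 1 h | 0 | 1.4% | 1.3% |
| 3 h | 0 | 4.2% | 3.7% |
| 8 h | 0 | 11.1% | 8.3% |

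Under the written rule, such a patient is recorded as having had no hypotension.

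**Step 3: other terms.** The a priori list contains hypotension, age, sex, emergency surgery, RCRI, postoperative GFR, day, and the day-by-hypotension interaction. None of the others carries intraoperative blood pressure. No section assigns intraoperative minutes to Day 0 or gives them a separate term.

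**Step 4: day label of a troponin.** Moving the origin from end to start shifts each boundary earlier by L, so the share of the 0–72 h postoperative period whose day label changes is L/24: 4.2% for 1 h, 12.5% for 3 h, 25% for 6 h and 33.3% for 8 h. For example, a troponin drawn 22 h after the end of a 3 h operation is 25 h after its start: Day 0 on one clock and Day 1 on the other. These are shares of time. They equal shares of samples only if sampling is uniform, whereas the plan describes irregular measurement.

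**The case against.** The strongest reply is that the intent is plain. The candidate-features text and Table 4 name a combined-period version. The single-period analyses are variants of the primary only if the primary uses both periods, and the a priori list introduces the days with an example marker, not as a closed definition. On this view the parenthesis in Data processing merely labels postoperative days. The point about intent stands: a reader might infer that the study will discard its intraoperative data, and the documents do not support that. But intent does not supply the missing rule. The only stated windows exclude surgery, and nothing says how combined-period time enters a day or over what denominator.

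A second reply is that stamps counted from surgery start do not conflict with windows counted from surgery end, since both times are extracted and conversion is a subtraction. That also stands. Start-referenced stamps alone are harmless.

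A reader might also infer that everything is timed from surgery start, or that the shares in Step 4 are troponins paired with the wrong day's exposure. Neither is supported. Cohort characteristics counts MINS time from the end of operation. Mispairing would need vital signs and troponin to be binned on different clocks, which no section states, and Primary Modeling describes their aggregation together. What remains is that the troponin day has no stated origin.

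**Conclusion.** The point holds as a defect in a stated rule. Applied as written, the windows exclude 100% of intraoperative minutes from the primary hypotension predictor. This needs no assumption about length of surgery. It contradicts Objective 1, makes the primary model the same as a planned variant, and removes the combined comparator for Objective 3. It should be settled before the daily variables are derived, because a choice made after seeing results would add analytic flexibility to the main exposure.

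The troponin part is a smaller ambiguity. Its size depends on length of surgery and on when samples are drawn, neither of which the documents give, so the Step 4 figures are illustrations only. The percentages in Step 2 likewise rest on the assumed one-third share and assumed lengths.

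**What to change.** Amend Data processing in three respects.

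1. **Put intraoperative time into the primary predictor.** One option is a Day 0 from surgery start to less than 24 h after surgery end, with Days 1 and 2 at 24–<48 h and 48–<72 h after surgery end, and the percentage computed over observed time in each window. Its drawback is that Day 0 varies in length with the operation. The alternative is a separate prespecified term for the intraoperative percentage below 75 mmHg. That fits the linear model: with RCRI as one score, the listed terms give 1 hypotension + 2 day + 2 interaction + 5 other = 10 coefficients, and one more makes 11, against a limit of 15. The binary model already lists 8 items against a limit of 8 variables, so a ninth would need a trade-off.
2. **Use the same surgery-end day boundaries** for vital signs, daily maximum troponin and MINS day.
3. **Clarify the surgery-start sentence**: it governs the time stamps and not the day windows. It need not be deleted.

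The cost is SAP wording and one re-derivation of the daily variables. No new data are needed, since operating-room entry and exit times are already in the Data Dictionary.

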Development and internal validation of models involving vital signs to predict troponin level and myocardial injury after noncardiac surgery: a single-centre retrospective cohort study

Introduction

The incidence of myocardial injury after noncardiac surgery (MINS) is approximately 12-15% and is associated with an increased risk of 30-day mortality (1), 1-year mortality (2), and 2-year major vascular events (3). Since more than 90% of patients with MINS are asymptomatic, routine troponin monitoring is required for detection (4). The postoperative days 0, 1, and 2 accounts for approximately 40%, 40%, and 10% of MINS, respectively (4). Presently, the Canadian Cardiovascular Society (CCS) perioperative guidelines recommend patients identified to be at risk according to the Revised Cardiac Risk Index (RCRI) and BNP/NT-proB-type Natriuretic Peptide (NT-proBNP) receive daily postoperative troponin monitoring for three days to identify MINS events (5). European and American societies have similar recommendations for troponin monitoring to detect MINS (6).

Current risk stratification models have multiple limitations (4). Most importantly, they predict an elevated risk over the postoperative period but cannot pinpoint when MINS may happen in the postoperative course given the patients' changing condition. Moreover, prescription of troponin monitoring is not universal (7), infrequent and inconsistent troponin monitoring may lead to delayed detection and management, and the rise of troponin is delayed by 3-4 hours from the time of injury (4).

Retrospective cohort studies show association amongst intraoperative and postoperative derangements in vital signs and MINS (4). Vital signs are routinely available within the electronic medical record, and may serve as objective predictors (i.e. as opposed to free text and disease names that have higher risks of misclassification and errors). Using both traditional longitudinal analysis techniques and novel methods in machine learning, we will investigate whether intraoperative and postoperative vital signs can enhance MINS surveillance by providing temporal prediction of MINS events.

Table 1. Preoperative factors studied in literature associated with MINS and/or major myocardial complication and mortality

Variable	References
Age	Goldman 1977 (8), Lee 1999 (9), Kheterpal 2009 (10), Botto 2014 (11), House 2016 (12)
Congestive heart failure	Lee 1999, Botto 2014
Coronary artery disease	Lee 1999, Kheterpal 2009, Botto 2014

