2. To develop and internally validate a model that uses the duration and degree of intraoperative and postoperative hypotension to predict daily probability of MINS or death (binary outcome, according to the 2021 American Heart Association (AHA) definitions (6) from postoperative days zero to two.
3. To evaluate how different definitions of hypotension affect the primary and secondary models above, and analyze the intraoperative and postoperative hypotension separately to determine whether intraoperative or postoperative hypotension alone are sufficient for prediction.
4. To explore whether other intraoperative and postoperative vital sign information (heart rate, oxygen saturation, and end-tidal carbon dioxide derangements at various definitions) add predictive value to the primary and secondary models above.
5. To use machine learning methods to perform exploratory analysis to determine 1) optimal methods for imputation for time series data; 2) visualization of time series data in the setting of prediction; 3) development and internal validation of machine learning models to use the time series data to predict troponin levels; and 4) to determine how many hours earlier than a binary MINS diagnosis were vital signs able

to predict a MINS diagnosis (as determined by when in the time series prior to MINS diagnosis that the model achieved various thresholds of predicted probability).

Methods

This is a single-center, retrospective cohort study on the development and internal validation of a prediction model.

Population

This study will include patients aged 45 years and older undergoing inpatient noncardiac surgery, who had MINS protocol ordered for postoperative high sensitivity troponin monitoring based on the CCS guidelines (5) from January 2020 to June 2021 (estimated sample size of 750, event rate of ~75).

Patients will be excluded if they do not have intraoperative and postoperative vital signs, or any postoperative troponin measurements. Patients who underwent repeat surgery or were readmitted within the first 72 hours postoperatively will be excluded, since patients who are discharged and readmitted will not have vital measurements as outpatients. If a patient had multiple admissions where the MINS protocol was ordered, only the first inpatient admission will be included. Patients who had positive troponin on postoperative day 4 will be excluded, since vital signs are only included up to postoperative day 3 for consistency.

Data sources

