Due to the longitudinal nature of the data, we need to include random effects to adjust for the dependence between within-patient daily observations. Thus, at minimum, we intend to include a random intercept corresponding to each patient within the model. However, we may consider including random slopes based on what is observed in the exploratory analysis of the vital signs data, though this would be limited by sample size. Since the effect of a vital signs covariate may be different depending on the day of monitoring, we will investigate interactions between the time predictor and vital signs predictors. This will be performed for only a small number of key time-varying predictors to avoid overfitting, given that the total

number of terms within the model will increase by at least 3 (if the interacting vital signs predictor is continuous or binary) for each additional interaction term included.

Visualizations of the effect of each predictor on the response will also be generated, to further investigate their relationships within the context of the model.

To summarize, a simplified example of the primary linear mixed effects model would be: $\text{Troponin} = \text{intercept} + b1\text{BP_day0} + b2\text{day1} + b3\text{day2} + b4\text{BP_day1*day1} + b5\text{BP_day2*day2} + \text{error}$ (plus other non-BP fixed-effect covariates as listed above). An example interpretation would be $b1$ will correspond to the effect of BP on Day 0, $b4$ will correspond to the additional effect of BP on Day 1 (with respect to Day 0) and $b5$ will correspond to the additional effect of BP on Day 2 (with respect to Day 0). However, we will perform exploratory analysis to explore other forms of longitudinal modeling to select the best model based on discrimination and calibration.

Survival analysis will not be employed due to the small variance in the days for the outcome (days 0-2). Also, right censoring is assumed in survival analysis, which does not apply in our case of troponin rise postoperatively as the majority of patients will not have a troponin increase eventually.

Secondary, Sensitivity, and Exploratory Analyses

In addition to the above outlined primary statistical analysis, we intend to conduct additional secondary, sensitivity and exploratory analyses to address Objectives 2 to 4 to examine how well the model performs given the following changes:

- Introduction of transformations or natural cubic splines on continuous predictors or outcomes

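### The stop rule for the binary MINS-or-death model omits the last troponin, so days after monitoring ended can enter as event-free although MINS status is unknown

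*Combined protocol and SAP*

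**What the plan says.** The Data processing section of the combined protocol and SAP gives two stop rules in adjacent sentences. For the continuous outcome, "the vital sign time series will be truncated at the last troponin measurement within 3 days of surgery". For the binary outcome, "the data will be truncated at the time of troponin laboratory diagnosis of the outcome event, postoperative day 3", with discharge and death as further stopping points and the earliest one applying. The last troponin is a stopping point only in the first rule.

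Other sections bear on this:

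- The Missing data section treats a patient as a complete case with one vital sign and one troponin. No troponin is required on each day.
- The Introduction says "Since more than 90% of patients with MINS are asymptomatic, routine troponin monitoring is required for detection".
- The Duration of data collection section expects monitoring to thin out by POD3 and limits the primary analysis to POD0 to POD2, partly for that reason.
- The Primary Modeling section says measurements come at irregular intervals, often because the physician is responding to the patient's condition. It rejects survival analysis partly because "right censoring is assumed in survival analysis, which does not apply in our case of troponin rise postoperatively".
- The truncation variants under Secondary, Sensitivity, and Exploratory Analyses are no truncation and a cut 12 hours before diagnosis. Neither stops at the last troponin.

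No section says what value the binary outcome takes on a day without a troponin.

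**The concern.** Take a patient with normal troponins on POD0 and POD1, no further draws, and discharge on POD4. Under the binary rule this patient's data run to POD3, so a POD2 record with blood pressure data can exist. On the plan's own account MINS is mostly silent and needs troponin to be found, so MINS status on that POD2 is unknown. If the record enters as event-free, an unknown is counted as a negative.

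The censoring statement points the same way. It argues that censoring is irrelevant because most patients never show a rise. A patient whose testing ends without an event before the end of POD2 is nevertheless right-censored for MINS.

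Objective 2 is the daily probability of MINS or death on POD0 to POD2, so the label on each day is the target itself. Cross-validated calibration would not expose the problem, because the observed outcomes carry the same labels as the training data. The decision curves use those labels too.

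**Working it through.** **Inputs.** The Population section gives "estimated sample size of 750, event rate of ~75". The Introduction and Primary Modeling put about 40%, 40% and 10% of MINS on POD0, POD1 and POD2. Two quantities are not in the documents and are assumed:

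- u: the share of event-free patient-days on a given POD that fall after the patient's last troponin.
- r: the risk on those days relative to tested days, taken from 0 to 1.

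**The plan's own figures.** The plan states no daily risk. It uses 750 and 75 only for its parameter caps, and these reproduce: 750/50 = 15 terms, and 75/10 = 7.5, rounded up to 8 variables.

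**Daily risk with every event-free patient kept.** Events are 75 × 0.40 = 30, 75 × 0.40 = 30 and 75 × 0.10 = 7.5.

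- POD0: 30/750 = 4.00%
- POD1: 30/(750 − 30) = 30/720 = 4.17%
- POD2: 7.5/(720 − 30) = 7.5/690 = 1.09%

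**Effect of coding untested days as event-free.** Let p be the risk on tested days. True risk over all event-free patients is (1−u)p + u·r·p. Coded risk is (1−u)p. Coded over true is therefore (1−u)/[(1−u) + u·r]. This equals 1−u when r = 1, and 1 when r = 0.

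With r = 1, true risk equals p = events/[at risk × (1−u)]:

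| Assumed u | POD1 (coded 4.17%) | POD2 (coded 1.09%) |
|---|---|---|
| 5% | 30/684 = 4.39% | 7.5/655.5 = 1.14% |
| 10% | 30/648 = 4.63% | 7.5/621 = 1.21% |
| 20% | 30/576 = 5.21% | 7.5/552 = 1.36% |
| 30% | 30/504 = 5.95% | 7.5/483 = 1.55% |
| 40% | 30/432 = 6.94% | 7.5/414 = 1.81% |

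With r = 0.5 and u = 20% on POD2, the ratio is 0.8/0.9 = 0.889, so true risk is 1.09%/0.889 = 1.22%.

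**Missed events.** On each day these number r × events × u/(1−u). Assume all of POD0 is tested, which leaves 30 + 30 + 7.5 = 67.5 detected events on POD0 to POD2. With r = 1:

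- u of 5% on POD1 and 10% on POD2: 1.58 + 0.83 = 2.4 (3.6% of 67.5)
- u of 10% and 20%: 3.33 + 1.88 = 5.2 (7.7%)
- u of 20% and 40%: 7.5 + 5.0 = 12.5 (18.5%)

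Halving r halves these counts; r = 0 makes them zero.

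**Simplifications.** Deaths and discharges are ignored, and missed cases are not carried forward in the next day's risk set.

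**The case against.** The strongest reply is that the documents never code an untested day as negative. Elsewhere truncation is described as a cut in the vital-sign or hemodynamic data, so the quoted rule may set only a predictor window. Primary Modeling aggregates troponin by day and indexes time by the day of measurement, and the binary model is introduced as a variant of that model. On this reading a day without troponin yields no row. This stands in part: a reader might infer that the plan definitely scores untested days as no MINS, and the text does not say so. But the tested-days-only reading fits poorly with the Outcome section, which counts a death before MINS diagnosis as an event without requiring a troponin that day. If it is what the sponsor intends, it still has to be written down.

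Second, every patient had the MINS protocol ordered, and that protocol monitors for three days. The remark that "infrequent and inconsistent troponin monitoring may lead to delayed detection and management" describes practice in general, not this cohort. This stands: nothing in the documents supports any particular untested share. It does not show that testing is complete, since one troponin is enough for inclusion and the plan itself expects irregular measurement.

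Third, the risk ratios only restate 1/(1−u). If testing stops mainly in stable patients, r is below 1 and the understatement shrinks. This also stands, and it is why a range is shown.

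Fourth, the Cohort characteristics section already reports the duration, number and frequency of troponin tests. That will describe the gaps, but it does not change who counts as at risk.

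**Conclusion.** The point holds as a defect in a stated rule that can bias a secondary model. It does not establish that the results will be wrong. The binary stop rule leaves out the last troponin, the label for an untested day is undefined, and no planned sensitivity analysis covers either.

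If later days enter as event-free and carry the same risk as tested days, daily risk is understated by the fraction u. At an assumed 20% untested, coded against true risk is 4.17% against 5.21% on POD1 and 1.09% against 1.36% on POD2. The bias is close to zero if monitoring is nearly complete, or if it stopped only in patients at negligible risk.

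A reader might also infer that the blood pressure association and the AUC are inflated, because testing follows the patient's condition and false negatives would gather among stable, normotensive patients. That is plausible, but the documents give no data on it and no calculation here shows it.

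**What to change.** In Data processing, end each patient's binary-model risk set at the earliest of first MINS, death, or the day of the last postoperative troponin (within POD2). Treat later days as missing, not as 0. Then:

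- State that an untested day between two tested days is kept and labelled from the next troponin. If that value meets the criteria, the event is dated to that draw, as the Outcome section already sets.
- Count deaths on POD0 to POD2 as events, report how many fall after the last troponin, and repeat the analysis without those. Keeping them while dropping survivors' later rows is asymmetric. The plan expects deaths within three days to be very rare.
- Report tested patient-days by POD, and keep the all-days version as a sensitivity analysis.
- In Primary Modeling, correct the statement that right censoring does not apply. The other reason given for not using survival analysis, the narrow spread of outcome days, can stand, so the model need not change.

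The cost is a few sentences and one filter on the patient-day dataset. Troponin and discharge times are already in the Data Dictionary. It lists in-hospital death only as yes or no, so the date of death must be obtained, but the plan's present rule needs that too. No MINS event is lost, since none can be diagnosed after the last troponin. The downside is fewer POD1 and POD2 rows, and results that apply to the period under troponin monitoring. That may be a higher-risk subset if testing follows the patient's condition.
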